#### 1.2 Secondary Objectives

There are four secondary objectives of the study:

**Safety Objective:** To demonstrate the safety of intravascular cooling in the management of acute traumatic SDH.

**Exploratory Objective**: To determine the effect of hypothermia on TBI biomarkers: glial fibrillary acid protein (GFAP) and ubiquitin C-terminal hydrolase (UCH-L1).

**Mechanistic Objective:** To determine if the incidence of cortical spreading depolarization is reduced in patients undergoing therapeutic hypothermia compared to patient undergoing normothermia.

**Impact on Resource Utilization Objective**: To determine the effect of moderate hypothermia on ICU length of stay (LOS) and hospital LOS.

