Exploratory analysis is to assess if therapeutic hypothermia will decrease blood/CSF levels of two TBI biomarkers. Two markers (GFAP and UCH-L1) will be interrogated. GFAP is a monomeric intermediate filament protein expressed by astrocytes that is released after TBI(34;35). Elevated serum GFAP level following severe TBI is predictive of poorer outcome and has shown to be correlated with intracranial pressure (ICP), mean arterial pressure (MAP), cerebral perfusion pressure (CPP), Glasgow Outcome Score (GOS) and mortality. GFAP serum concentrations above a cut-off level of 1.5 μg/L were predictive of death or poor outcome (GOS at 6 months) with 85% sensitivity and 52% specificity, and 80% sensitivity and 59% specificity, respectively(35). UCH-L1 is a 24kDa protein thought to be involved with the removal of oxidized or misfolded proteins(36). It has been associated with neurodegenerative diseases and brain ischemia(37). UCH-L1 has been detected in both CSF and serum within 6 hours of injury, it has distinguished injury severity and predicted death(37;38).

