Following placement of the electrode, the lead will be externalized through the dura and craniotomy. If the bone flap is replaced, the lead will be exteriorized through a burr hole to facilitate subsequent removal. Furthermore, the lead wire will be exteriorized in a straight line with the electrode strip, also to facilitate removal. Finally, the lead is tunneled under the scalp and out through a stab wound distant from the craniotomy incision line in order to reduce the risk of infection. When ECoG recordings are complete, the strip is removed by gently pulling it through the stab wound followed by watertight closure of the skin incision.

The technique of ECoG strip placement is a standard surgical procedure in epilepsy neurosurgery, and has been used as described to monitor surgical patients with severe stroke or traumatic brain injury at more than a dozen neurosurgical centers.(41-45)

Upon admission to the neuro-intensive care unit (NICU), following surgery, the leads from the ECoG electrode strip will be connected to an EEG amplifier. External ground and reference electrodes will be placed and continuous ECoG recordings will then commence. The reference electrode is a platinum needle placed under the scalp.

Continuous ECoG monitoring will be performed for at least the same duration as ICP monitoring. In patients randomized to hypothermia, this is until at least 24 hours after re- warming is complete. In normothermia patients, patients will be monitored a minimum of 96 hours, and longer if continued ICP monitoring is clinically indicated. When monitoring is complete, the electrode strip will be removed at the bedside under sterile conditions, as is performed for standard-of-care intracranial devices.

Blood samples for biomarker analysis will be taken at 3 time points (T1, within 6 hrs and as close to time of injury as possible (pre-hypothermia for the treatment arm); T2, post-surgical evacuation of hematoma (7-48 hrs); T3, 5-14 days post-injury or DC whichever comes first. If the patient has a ventricular drain in place, CSF samples will also be collected.

As part of standard care all patients are expected to have an intracranial pressure monitor (either extraventricular drain or intraparenchymal monitor).

**5.3.2 Prohibited Interventions.** Please see re-warming protocol regarding fluids and electrolytes.

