# 6.2.2 On-Study/On-Intervention Evaluations

Within 6 hours of injury (T1)

Blood (and CSF if available) should be collected

Up to 2 liters IV fluid administered

Placement of intravascular catheter

Cooling to 35°C for hypothermia arm; 37°C for normothermia

Opening of dura (followed by evacuation of SDH)

Adverse events monitored

• >6 to 48 hours post-injury (T2)

Following hematoma evacuation and hemostasis ECoG Electrode strips should be placed

Upon admission to the ICU, following surgery, the leads from the ECoG electrode strip will be connected to an EEG amplifier. External ground and reference electrodes will be placed and continuous ECoG recordings will then commence.

Repeat head CT as indicated for clinical care

Temperature maintenance of 33°C for hypothermia arm; 37°C for normothermia arm

Blood (and CSF if available) should be collected

Adverse events monitored

>48 hours to 5 days

Rewarming initiated according to rewarming protocol (37°C for normothermia arm)

Continuous ECoG monitoring will be performed for at least the same duration as ICP monitoring. In patients randomized to hypothermia, this is

until at least 24 hours after re-warming is complete. In normothermia patients, patients will be monitored a minimum of 96 hours, and longer if continued ICP monitoring is clinically indicated. When monitoring is complete, the electrode strip will be removed at the bedside under sterile conditions, as is performed for standard-of-care intracranial devices.

Adverse events monitored

(±0.5°C for all temperatures)

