#### **9.2.2 Secondary outcomes.** Secondary outcomes will include:

- adverse event rates (e.g., infection, pneumonia, hemorrhage, thrombosis)
- ICU LOS, hospital LOS
- incidence of cortical spreading depolarization

• levels of biomarkers (e.g., GFAP, UCH-L1)

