# 9.5 Data Analyses

The primary analysis population will be an Intention-to-Treat population, all randomized subjects, followed by an As-Treated analysis for sensitivity. As described below, for the primary outcome, 4-week DRS will be used to impute missing 6-month GOSE for the interim analyses. Demographic and baseline laboratory results will be summarized using descriptive statistics, including means, standard deviations, medians, ranges, histograms and box-plots. Fisher's exact test and Wilcoxon rank sum test will be used in the data analyses of categorical and continuous variables, respectively. Adverse events will be reported by type, frequency and severity.

9.5.1 Statistical Modeling. The National Acute Brain Injury Study: Hypothermia II (NABIS:H II) shows that there was a strong correlation between 4-week Disability Rating Scale (DRS) and 6month GOSE (Table 1). In particular, there were 2 false negatives out of 45 patients (4%) and 6 false positives out of 30 patients (20%). It shows that the short-term response is a good predictor for 6-month GOSE.

Table 3 summarizes the historical data (NABIS:H II study) comparing the 4-week DRS score and 6-month outcome; 80% (24/30) of good short-term DRS had a good long-term GOSE, while 4% (2/45) poor DRS had a good GOSE:

Table 3

	6-month GOSE		
4-week DRS Score	Poor	Good	Total
Poor (19 or larger)	43 (96%)	2 (4%)	45
Good (18 or less)	6 (20%)	24 (80%)	30

The statistical model used in this study explicitly models the relationship between 4-week DRS and 6-month GOSE score. Let pDc and pDt be the probabilities of good 4-week DRS scores in the control and treatment groups. Furthermore, define

 $p_{Gc0} = Pr(GOSE good | control, DRS poor)$ 

 $p_{Gc1} = Pr(GOSE good | control, DRS good)$ 

pGt0 = Pr(GOSE good | treatment, DRS poor)

pGt1 = Pr(GOSE good | treatment, DRS good)

These probabilities define the conditional probabilities of achieving a good GOSE score given the DRS score and treatment group.

Together, pDc, pDt, pGc0, pGc1, pGt0, and pGt1 define a joint distribution over DRS and GOSE scores. The key parameter of interest is the probability of a good GOSE score within each group, which can be derived from these parameters.

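### The only method stated for biomarker levels is an unadjusted rank-sum test that makes no use of the T1 sample. It is valid, but it discards precision.

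*Combined protocol and SAP*

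**What the plan says.** Section 1.2 sets an exploratory objective, "To determine the effect of hypothermia on TBI biomarkers", and Section 2.2 gives its direction: "Exploratory analysis is to assess if therapeutic hypothermia will decrease blood/CSF levels of two TBI biomarkers". Section 9.2.2 lists "levels of biomarkers (e.g., GFAP, UCH-L1" among the secondary outcomes.

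Section 5.3.1 (and the Synopsis) schedules three samples:

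- **T1:** "T1, within 6 hrs and as close to time of injury as possible (pre-hypothermia for the treatment arm".
- **T2:** "T2, post-surgical evacuation of hematoma (7-48 hrs". Section 6.2.2 words the same window as ">6 to 48 hours post-injury (T2", a small inconsistency to reconcile.
- **T3:** between 5 and 14 days after injury, or at discharge if that is earlier.

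CSF is taken only from patients with a ventricular drain.

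On analysis, Section 9.5 says: "Fisher's exact test and Wilcoxon rank sum test will be used in the data analyses of categorical and continuous variables, respectively". For biomarkers it names no baseline covariate, change score, longitudinal model, sampling-time term, principal time point or rule for missing samples.

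**The concern.** The biomarker question asks whether cooling lowers the level of a marker measured before and after treatment starts. Section 2.2 itself says that UCH-L1 is detectable within 6 hours of injury and distinguishes injury severity, and that GFAP predicts outcome. A T1 value should therefore carry severity information that explains some of the spread at T2 and T3. Randomization is blocked by site and not stratified by severity, so that spread stays in the error term of an unadjusted comparison. The trial may also be small: it is intended for 120 patients and can stop for futility at 31 or 60.

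What is at stake is the chance of seeing a real biomarker effect, and the width of the interval around it. The T1 samples are collected in any case, so leaving them out of the comparison gives up information at no saving.

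**Working it through.** **The plan's own figure.** There is none to reproduce. The documents give no SD, effect size, significance level or power for the biomarkers. Everything below rests on assumed values.

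**Inputs.** From the documents: 60 per arm (120 intended, 1:1, Section 9.3) and a T2 window of 7 to 48 hours, a span of 48 − 7 = 41 hours. Assumed: correlation r between log T1 and log T2 of 0.3, 0.5 or 0.7; two-sided 0.05; 80% power; log-scale SD of 1.

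**Step 1: variance.** Adjusting for T1 multiplies the variance of an unadjusted difference in means by 1 − r². The equivalent gain in patients is 1/(1 − r²) − 1.

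| r | 1 − r² | Variance cut | Equivalent extra patients |
|---|---|---|---|
| 0.3 | 0.91 | 9% | 10% |
| 0.5 | 0.75 | 25% | 33% |
| 0.7 | 0.51 | 49% | 96% |

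**Step 2: detectable difference at 60 per arm.** An unadjusted comparison of means detects d = (1.960 + 0.842) × √(2/60) = 0.511 SD. The rank-sum test has efficiency 3/π under normality, so it detects 0.511/√(3/π) = 0.52. ANCOVA on T1 detects 0.511 × √(1 − r²) = 0.49, 0.44 or 0.37 for r = 0.3, 0.5 or 0.7. This step compares ANCOVA with the rank-sum test itself.

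**Step 3: simulated power at 60 per arm for d = 0.5.** There were 2,000 trials per cell, with T2 uniform on 7 to 48 hours. Each range runs over no decay, a 48 h half-life and a 24 h half-life.

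| r | Rank-sum, levels | Rank-sum, change from T1 | ANCOVA, T1 | ANCOVA, T1 and sampling time |
|---|---|---|---|---|
| 0.3 | 0.70–0.76 | 0.57–0.62 | 0.75–0.82 | 0.80–0.81 |
| 0.5 | 0.70–0.76 | 0.70–0.75 | 0.82–0.89 | 0.87–0.89 |
| 0.7 | 0.70–0.75 | 0.88–0.93 | 0.93–0.97 | 0.96–0.97 |

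A rank-sum test on change from T1 is not a safe substitute. At r = 0.3 it does worse than ignoring T1.

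**Step 4: validity.** With no treatment effect, equal timing in both arms, r = 0.5 and a 24 h half-life (4,000 trials), the rank-sum test rejected in 0.043 of trials, against a nominal 0.05.

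**Step 5: sampling time.** An assumed 24 h half-life implies a 2^(41/24) = 3.3-fold difference between a 7 h and a 48 h sample. A 48 h half-life implies 2^(41/48) = 1.8-fold. With equal timing by arm this is only noise: rank-sum power is about 0.70 with a 24 h half-life, against 0.75–0.76 with no decay. If T2 were drawn later in one arm by an assumed 3, 6 or 12 hours, with r = 0.5 and no true effect, the rejection rates were:

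| Half-life | Rank-sum, levels | ANCOVA, T1 only | ANCOVA, T1 and time |
|---|---|---|---|
| 48 h | 0.06 / 0.07 / 0.12 | 0.06 / 0.09 / 0.15 | 0.05 / 0.05 / 0.06 |
| 24 h | 0.07 / 0.13 / 0.33 | 0.07 / 0.16 / 0.42 | 0.04 / 0.05 / 0.05 |

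Adjusting for T1 alone does not protect against unequal timing, so a time-adjusted analysis is useful as a check.

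**The case against.** The strongest case on the other side is that the plan has not chosen a wrong test; it has left the biomarker analysis unspecified. The quoted sentence is generic, does not name biomarkers, and does not say whether ranks are taken on levels or on change from T1. The objective is exploratory, carries no power claim, and plays no part in the stopping rules or the GOSE test. The gain depends on an unknown correlation and is small at r = 0.3. The 1 − r² figure also compares ANCOVA with a difference in means, not with the rank-sum test.

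Most of this stands as a limit on size. It does not remove the point: the rank-sum test is the only method the plan gives for a continuous outcome, and no use of T1 is stated anywhere. Step 2 makes the direct comparison with the rank-sum test.

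Four stronger readings are tempting, and the documents do not support them:

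- **That the rank-sum result would be biased or invalid.** It is valid under randomization with similar timing by arm, and the test already allows for chance imbalance in severity. Bias would need T2 timing to differ by arm, which the documents neither show nor exclude.
- **That T1 is a pre-treatment baseline in both arms.** Section 5.3.1 and the Synopsis say so only for the treatment arm. Section 6.2.1 merely permits a pre-entry draw, and Section 6.2.2 lists the T1 collection alongside fluids and catheter placement.
- **That draw times are already available.** Section 6.3.8 describes labels with subject number, sample type and time point. Nothing states that the clock time of the draw is recorded.
- **That sampling time belongs in the main model.** It arises after randomization. At T3 it can be set by discharge, and hospital length of stay is itself an outcome.

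**Conclusion.** The point holds as a loss of precision, not as an error of validity. By default the plan compares GFAP and UCH-L1 levels with an unadjusted rank-sum test and makes no use of T1. Adjusting for T1 would cut variance by about 9% to 49% relative to an unadjusted comparison of means for an assumed correlation of 0.3 to 0.7. At 60 per arm the detectable difference would fall from 0.52 SD to between 0.49 and 0.37 SD. These sizes assume roughly normal log values and a T1 unaffected by treatment in either arm. The correlation and the decay rates are assumptions; neither is in the documents. The change is worth making because it is cheap, but it concerns an exploratory objective only.

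**What to change.** Add a short biomarker paragraph to Section 9.5:

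1. Analyse log GFAP and log UCH-L1 at T2 and T3 by ANCOVA, or by a mixed model over both times, with arm and log T1 as covariates.
2. Keep the rank-sum test on levels as a sensitivity analysis.
3. State how patients without a T1 value are handled, with blood and CSF treated separately.
4. Confirm, and state, that T1 is drawn before any study intervention in both arms. If control samples can be later, say so and treat the T1 adjustment with caution.
5. Establish whether clock times of injury and of each draw are recorded. If they are, add hours from injury to sample as a sensitivity analysis only, reported with and without the term, and with particular care at T3.

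The T1 adjustment costs a change of wording and needs no new samples, visits or patients. The time-adjusted analysis may need a data-collection change if draw times are not captured. The downsides are a distributional assumption on the log scale, which the retained rank-sum test checks, and the need for a rule on missing T1.

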# The HOPES Trial Version 5 02/23/2018

and death as poor outcomes) at 6 months post-injury will be the primary outcome. Disability Rating Scale (DRS) at 4 weeks will be used to impute missing GOS/GOSE scores and will be incorporated into the Bayesian monitoring model.

Patients will have blood and CSF (when available) samples taken at 3 time points [T1, within 6 hrs and as close to time of injury as possible (pre-hypothermia for the treatment arm); T2, post-surgical evacuation of hematoma (7-48 hrs); and T3, 5-14 days post-injury or discharge (DC)], whichever comes first.

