#### 9.2 Outcomes

**9.2.1 Primary outcome**. Primary outcome is GOSE at 6 months±3weeks post injury. GOSE (dichotomous: Good recovery and moderate disability will be designated as favorable outcomes; severe disability, vegetative state, and death as poor outcomes) at 6 months post-injury will be the primary outcome. Disability Rating Scale (DRS) at 4-6 weeks will be used to impute missing GOS/GOSE scores for futility analysis. Outcome scales will be assessed by an evaluator who is blind to study group assignment.

Glasgow Outcome Scale-Extended (GOSE) is a widely used global outcome score including 8 categories: dead, vegetative state, lower/upper severe disability, lower/upper moderated disability, lower/upper good recovery(47). GOSE assesses consciousness, independence, work status, return of lifestyle via a structured interview. It is relatively easy to administer and has good interrater reliability and content validity. (Appendix II)

Disability Rating Scale (DRS) is a global outcome scale that measures the level of arousal, cognitive ability related to activities of daily living and level of functioning. It includes eye opening, communication ability, motor response, feeding, toileting, grooming and employability(48). Scores range from 0 (no disability) to 29 (profound vegetative state) and death is scored at 30. It has been shown to be a good predictor of later outcome with the one month exam having an 87% correlation with the 6 month GOSE(12). (Appendix III)

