We estimate these parameters in a Bayesian fashion, placing Beta(2,3) priors on pDc and pDt, Beta(1,4) priors on pGc0 and pGt0, and Beta(4,1) priors on pGc1 and pGt1. These priors reflect the historical data but are weak in that each prior has 5 observations worth of weight, meaning that accumulating data in contrast to the historical data above will result in inferences based on the current data, not the historical data. Thus this model is sufficiently flexible that it may be used when DRS is highly predictive of GOSE and also may be used if DRS is not predictive of GOSE.

The final analysis is a one-sided Fisher exact test with significance level 0.02 conducted only on the GOSE scores. Thus, the DRS values are only used in the analysis to predict GOSE scores for subjects who have a DRS score but not a GOSE score. For the final analysis, 6-month GOSE scores will be used. If the 6-month GOSE score is missing the 4-week DRS score will be used to impute the 6-month GOSE score.

At each interim analysis we compute two predictive probabilities. The first is the predictive probability of trial success if enrollment stops, the current subjects are followed to completion, and the Fisher's exact test is conducted on the final data. For this predictive probability many of the subjects will have 6-month GOSE scores reported. The uncertainty in the predictive

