The operating characteristics of this design (type I error, power, and expected sample size) were computed by simulation in a variety of possible scenarios. These scenarios were constructed by crossing four possible treatment effects with two possible relationships between 4-week DRS and 6-month GOSE scores (predictive and nonpredictive). Table 5 shows the values of the parameters for each of the simulated scenarios. In all scenarios the probability 6- month GOSE is good in the control arm is 0.347. In the *null* scenarios, scenarios where there is no difference between the scores, the probability 6-month GOSE is good in the treatment arm is also 0.347 (no treatment effect). We also consider low scenarios where the probability 6-month GOSE is good in the treatment arm is 0.498, medium scenarios where the probability 6-month GOSE is good in the treatment arm is 0.536, and alternative scenarios where the probability 6- month GOSE is good in the treatment arm is 0.604. The trial is powered for values closer to the 0.604 6-month scenario.

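### The final Fisher test imputes missing 6-month GOSE from 4-week DRS by an unstated method, other sections tie that imputation to interim work, and no simulation covers it

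*Combined protocol and SAP*

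**What the plan says.** Four places describe the use of DRS for missing GOSE, and they do not agree.

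- **Section 9.5.1, final analysis.** "The final analysis is a one-sided Fisher exact test with significance level 0.02 conducted only on the GOSE scores". Two sentences later: "If the 6-month GOSE score is missing the 4-week DRS score will be used to impute the 6-month GOSE score".
- **Section 9.2.1.** DRS at 4-6 weeks "will be used to impute missing GOS/GOSE scores for futility analysis".
- **Section 9.5, opening paragraph.** "4-week DRS will be used to impute missing 6-month GOSE for the interim analyses".
- **Synopsis, Design and Outcomes.** "Disability Rating Scale (DRS) at 4 weeks will be used to impute missing GOS/GOSE scores and will be incorporated into the Bayesian monitoring model". This is not limited to interim looks.

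Section 9.5.1 also defines arm-specific probabilities of a good GOSE given the DRS class, with Beta priors, for the interim predictions. It does not say whether the final imputation uses that model, carries the DRS class over at the 18/19 cut of Table 3, or does something else. No pooling rule, expected share of missing GOSE or missing-data sensitivity analysis is given. The eight scenarios of Table 5, and so the operating characteristics of Table 6, have no missing GOSE.

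**The concern.** The rule sits inside the only confirmatory test, a binary comparison at one-sided 0.02. Two statisticians could take different primary analyses from this text, and the choice between them should not be open once outcomes are known.

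Whatever value is filled in, Fisher's test as described counts it as an observed outcome. A carried-over DRS class measures something other than 6-month GOSE: in the historical data "80% (24/30) of good short-term DRS had a good long-term GOSE, while 4% (2/45) poor DRS had a good GOSE". A single random draw from a model has the right average but hides the uncertainty of the draw. At stake are power, the size of the estimated effect and, in some situations, type I error. Table 6 cannot settle this, because it was computed without missing outcomes.

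**Working it through.** **Inputs.** Table 5: good-DRS probability 0.40 (control) and 0.74 (treatment) in Alt Pred, 0.50 in both arms in Alt Non; probability of good GOSE 0.045 after poor DRS and 0.800 after good DRS in the predictive scenarios. Section 9.5.2: "In all scenarios the probability 6- month GOSE is good in the control arm is 0.347", and 0.604 on treatment in the alternative scenarios. Final test: one-sided Fisher at 0.02. **Assumed, because the documents do not give them:** share of missing GOSE 5% to 20%, missing at random within arm; accrual 2.5 patients per month.

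**1. The plan's own figures.**
- Control: 0.40 × 0.800 + 0.60 × 0.045 = 0.347.
- Alt Pred treatment: 0.74 × 0.800 + 0.26 × 0.045 = 0.604. The difference is 0.257.
- The adaptive design was simulated without missing data (looks at 60 to 300, Table 4 thresholds, Section 9.5.1 priors, simple randomisation, 2-3 patients per month). Alt Pred success was 0.941-0.945 (stated 0.942), Alt Non 0.918-0.922 (stated 0.917), Null Pred 0.020-0.024 (stated 0.024) and Null Non 0.017-0.020 (stated 0.021). The rows used below are reproduced closely enough.

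**2. Bias under carry-over.** Among imputed patients the expected difference is pDt − pDc.
- Alt Pred: 0.74 − 0.40 = 0.34 instead of 0.257. At 20% missing the overall difference is 0.8 × 0.257 + 0.2 × 0.34 = 0.274.
- Alt Non: 0.50 − 0.50 = 0 instead of 0.257. At 20% missing the overall difference is 0.8 × 0.257 = 0.206.

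**3. Power in the full adaptive design** (5,000 trials per cell, standard error at most 0.007).

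| Scenario | Missing | Carry-over | Observed GOSE only | Stated, none missing |
|---|---|---|---|---|
| Alt Non | 10% | 0.889 | 0.900 | 0.917 |
| Alt Non | 20% | 0.807 | 0.895 | 0.917 |
| Med Non | 20% | 0.591 | 0.687 | 0.756 |
| Alt Pred | 10% | 0.943 | 0.919 | 0.942 |
| Alt Pred | 20% | 0.942 | 0.884 | 0.942 |

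**4. Type I error in the full adaptive design** (10,000 trials per cell; limit 0.025).

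| Null situation | Missing (treatment / control) | Carry-over | Observed GOSE only |
|---|---|---|---|
| Null Pred | 10% / 10% | 0.017 | 0.017 |
| Null Pred | 20% / 20% | 0.016 | 0.013 |
| Null Non | 20% / 20% | 0.013 | 0.014 |
| Null Pred | 20% / 5% | 0.022 | 0.016 |
| Null Non | 20% / 5% | 0.026 | 0.019 |
| DRS shifted, GOSE null | 5% / 5% | 0.024 | 0.018 |
| DRS shifted, GOSE null | 10% / 10% | 0.024 | 0.016 |
| DRS shifted, GOSE null | 20% / 20% | 0.043 | 0.016 |

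The shifted scenario is not in Table 5. It sets good DRS at 0.40 against 0.60 and keeps the treatment GOSE rate at 0.347 by taking (0.347 − 0.40 × 0.045) / 0.60 = 0.548 as the probability of good GOSE after good DRS. The 0.026 in Null Non has a standard error of 0.0016, so it cannot be told apart from 0.025.

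**5. Single draw from the Section 9.5.1 model, counted as observed.** At fixed N = 120 with 20% missing, the Null Non rejection rate is about 0.03, above the test's nominal 0.02. The draw is not biased in the way carry-over is. The excess arises because imputed values enter the test as if they were data.

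**The case against.** **Carry-over is not written.** A reader might infer that the DRS class simply replaces GOSE. The text says only that DRS is used to impute, in the section that defines the conditional model, so a model-based reading is at least as natural. This stands: the figures in steps 2 to 4 are conditional on carry-over. It does not rescue the rule, since a single model draw treated as observed has its own problem (step 5) and the plan does not say which method is meant.

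**The sections are not strictly exclusive.** A reader might infer that Sections 9.2.1 and 9.5 forbid DRS in the final test. Neither says so outright, Section 9.5 points forward to the detail below it, and the Synopsis is unrestricted. The finding is therefore inconsistency, not breach of a prohibition, and deleting the Section 9.5.1 sentence alone would leave the Synopsis in conflict.

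**Large losses are tempting to quote.** At fixed N = 120 and 20% missing, carry-over takes Alt Non power from 0.716 to about 0.50. That ignores the adaptive design, and observed-only analysis at the same N gives about 0.615, so nearly half of the fall comes from the missing data themselves: (0.716 − 0.615) / (0.716 − 0.50) = 0.47.

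**General type I inflation is not supported.** With equal missingness the plan's own null scenarios show none. Nor do the documents say that imputed GOSE would enter the Section 2.1 assessment of DRS as a predictor; circularity there is a risk to exclude, not a stated plan.

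**The missing rate is assumed.** This also stands. Section 2.2 quotes 40-70% mortality in surgical subdural hematoma, and early death fixes both scales. Missing GOSE would then fall mainly among survivors, and complete independence of DRS and GOSE is a stress case, although it is one that the plan simulates.

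**Conclusion.** The concern holds as an inconsistency and an unspecified method inside the confirmatory test, with conditional consequences.

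- Under carry-over the effect among imputed patients is overstated when DRS is predictive and erased when it is not.
- With 20% missing, Alt Non power is about 0.81 against 0.895 on observed GOSE. At 10% the gap is about one point, close to simulation error.
- Type I error exceeds 0.025 clearly only if treatment moves 4-week DRS without moving 6-month GOSE and about 20% of GOSE is missing (about 0.043). At 5-10% it stays at 0.024.
- A single model draw counted as observed can also raise type I error, to about 0.03 in Null Non at fixed N = 120 with 20% missing.

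All sizes rest on the assumed missing rates, on missingness at random within arm and, for the adaptive figures, on the assumed accrual. They do not show that the trial's type I error is uncontrolled. They do show that Table 6 says nothing about the rule as written, and that the rule should be settled before outcomes are known.

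**What to change.** 1. Make the Synopsis, Section 9.2.1, the opening of Section 9.5 and Section 9.5.1 agree on where DRS is used.
2. Replace the Section 9.5.1 sentence with one primary rule. Known deaths count as poor. Remaining missing GOSE is multiply imputed from the arm-specific model for good GOSE given DRS already defined there, with a stated pooling rule that carries imputation uncertainty into the test. State what happens when DRS is missing too.
3. Report Fisher's test on observed GOSE only as a sensitivity analysis.
4. Assess DRS as a predictor of GOSE on observed GOSE only.
5. Add missing-GOSE scenarios to the Table 5 and 6 simulations, so that the 0.02 level is checked under the rule to be used.

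The cost is wording, some code and new simulation runs; no new data are needed. When DRS is predictive, power will be slightly less favourable than under carry-over, whose advantage there comes from overstating the effect. Observed-only is better kept as sensitivity than made primary, because in Alt Pred at 20% missing it gives 0.884 against 0.942.
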